The members listed on the IRB protocol will be the only individuals who have access to the data. Drs. [name] and [name] will be the only member to have access to the code which links the participants to their data.

- f) **If data or specimens will be coded, describe the method in which they will be coded so that study participants' identities cannot be readily ascertained from the code.**

Each participant will randomly be assigned a code which contains a letter and number, generated by a random number generator. These data will be kept in Redcap and will otherwise not be accessible.

Title : Effect of Night Float Call on Sleep and Activity Patterns Among Anesthesia Residents
Approval Period: 08/19/2020 - 12/31/2999

g) If data or specimens will be coded, indicate who will maintain the key to the code and describe how it will be protected against unauthorized access.

Our data collected will be immediately coded for analysis. Drs. [name] and [name] will be the only member to have access to the code which links the participants to their data. These data will be kept in Redcap and will otherwise not be accessible.

h) If you will be sharing data with others, describe how data will be transferred (e.g., courier, mail) or transmitted (e.g., file transfer software, file sharing, email). If transmitted via electronic networks, describe how you will secure the data while in transit. See <http://www.stanford.edu/group/security/securecomputing/>. Additionally, if you will be using or sharing PHI see <https://uit.stanford.edu/security/hipaa>

Data will be transferred via secure Stanford webmail and Stanford Box

i) How will you educate research staff to ensure they take appropriate measures to protect the privacy of participants and the confidentiality of data or specimens collected (e.g. conscious of oral and written communications, conducting insurance billing, and maintaining paper and electronic data)?

All of our research team are or will be up to date on CITI training before initiation of the study.

12. Potential Conflict of Interest

Investigators are required to disclose any financial interests that reasonably appear to be related to this protocol.

Financial Interest Tasks

Investigators	Role	Email	Has Financial Interest?	Date Financial Interest Answered	Date OPACS Disclosure Submitted	Date OPACS Review Completed
[name]	PD	[contact]	N	05/21/2019		
[name] [name]	COP D	[contact]	N	05/21/2019		
[name]	FS	[contact]	N	05/19/2019		

13. Consent Background

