Title : Effect of Night Float Call on Sleep and Activity Patterns Among Anesthesia Residents
Approval Period: 08/19/2020 - 12/31/2999

Modification Form	3
Personnel Info	3
Participant Population	4
Study Location	4
General Checklist	5
Funding	7
Resources	7
Expedited Category	8
Purpose	9
Radioisotopes or Radiation Machines	12
Drugs, Reagents, Chemicals, Devices	12
Medical Equipment for Human Subjects and Laboratory Animals	13
Participant Population(a-g)	13
Participant Population(h-m)	14
Risks(a-d)	15
Privacy And Confidentiality	16
Conflict Of Interest	18
Consent Background	18
Assent Background	19
Hipaa	19
Attachments	19

Title : Effect of Night Float Call on Sleep and Activity Patterns Among Anesthesia Residents
Approval Period: 08/19/2020 - 12/31/2999

[Obligations](#) 19

Title : Effect of Night Float Call on Sleep and Activity Patterns Among Anesthesia Residents
Approval Period: 08/19/2020 - 12/31/2999

Modification

1. Summarize your proposed changes.

The proposed changes to our protocol include: 1) recruitment of additional participants, 2) expanding the number of rotations which residents can be recruited, 3) adding additional COVID-19 cleaning protocols for the Fitbits, and 4) adding an additional investigator to the protocol ([name]). We have enrolled twelve participants in the study to date, and we are hoping to enroll an additional 40 more participants to adequately power our study. Previously, we were only recruiting anesthesia residents who were rotating on the general OR rotation, but we would also like to follow them when they are on their OB anesthesia rotation as they also do night float shifts during that rotation. The consent form has been updated to include the additional rotations that will be recruited, but no changes need to be made for the previously enrolled participants

2. Indicate Level of Risk

No Change

3. Update the Conflict of Interest (COI) section if any changes in COI have been made since the last protocol submission.

N Is there a change in the conflicting interest status for any existing personnel on this protocol?

Protocol Director

Name [name]		Degree (Program/year if student) MD		Position, e.g. Assistant Professor, Resident, etc. Clinical Instructor
Department Anesthesia	5640	[contact]	[contact]	E-mail [contact]
CITI Training current				Y

Admin Contact

Name [name]		Degree (Program/year if student)		Position, e.g. Assistant Professor, Resident, etc. Clinical Instructor

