Title : Effect of Night Float Call on Sleep and Activity Patterns Among Anesthesia Residents
Approval Period: 08/19/2020 - 12/31/2999

Explain whether you will have sufficient time to conduct and complete the research. Include how much time is required.

The planned time course of this project is 2 years. We will aim to collect between responses from 40-60 participants (each night float lasts 1 week and there will be one week run in before and one week of post call activities to evaluate effects). We will continually de-identify, process and analyze data to assure that analysis programs are intact.

e) Access to target population.

Explain and justify whether you will have access to a population that will allow recruitment of the required number of participants.

The participants in the study will be residents within the Stanford University Department of Anesthesia who choose to participate in this study of the effect of call on activity and sleep. There are 4 residents on each rotation per month, so between the general OR and OB anesthesia rotations, we could recruit up to 8 participants per month in order to enroll our target number of participants

f) Access to resources if needed as a consequence of the research.

State whether you have medical or psychological resources available that participants might require as a consequence of the research when applicable. Please describe these resources.

A possible consequence of the research is that participants become more aware of different night float systems can affect their sleep and activity which may affect their attitude towards call. We have a strong PRIME (resiliency in medical education) program within the department that can support the residents if they feel any symptoms of burnout. There is always the remote possibility of identifiable data release. We are putting processes into play including secure data storage in Redcap and immediate de-identification at the end of each resident's participation.

g) Lead Investigator or Coordinating Institution in Multi-site Study.

Please explain (i) your role in coordinating the studies, (ii) procedures for routine communication with other sites, (iii) documentation of routine communications with other sites, (iv) planned management of communication of adverse outcomes, unexpected problems involving risk to participants or others, protocol modifications or interim findings.

Expedited Form

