- b) State what the Investigator(s) hope to learn from the study. Include an assessment of the importance of this new knowledge.**

We will learn how different lengths of night float affects a resident's activity level, sleep and self reported wellness. These objective measurements can be used to assess targets for intervention with an altered call paradigm or increased support to prevent long term disability from changes identified. In the long term, we hope to reduce physician burnout and improve physician wellness.

- c) Explain why human subjects must be used for this project. (i.e. purpose of study is to test efficacy of investigational device in individuals with specific condition; purpose of study is to examine specific behavioral traits in humans in classroom or other environment)**

The purpose of the study is the examine specific behavioral patterns, specifically sleep pattern and activity level, in humans who are working during a night shift system.

2. Study Procedures

- a) Please SUMMARIZE the research procedures, screening through closeout, which the human subject will undergo. Refer to sections in the protocol attached in section 16, BUT do not copy the clinical protocol. Be clear on what is to be done for research and what is part of standard of care.**

Participants will be recruited via an email once they are scheduled for a week of night float in the Stanford Main Operating room or Obstetric anesthesia. Potential participants who are taking prescription medications that might affect their alertness during the study period will not be enrolled.

We will quantify the changes in sleep pattern and activity during the week before, during, and after the night float call week. Self reported aspects of well being including fatigue, physical function, and positive affect will be assessed with NIH PROMIS surveys at the end of each week during the study period.

We will use the Fitbit Alta HR to quantify the change in total amount of sleep, sleep interruption and sleep phase and steps per day. Data will be analyzed only when it is coincident with heart rate data to correct for periods when the device is not used.

Activity will not alter from the participants normal except that they will wear the Fitbit and respond to the NIH PROMIS surveys over the study period. After completing all surveys and returning the fitbit, the participants will receive a \$10 gift certificate as a recognition for their time.

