Based on their rotation schedule, they will have the option to wear the Fitbit for an additional 3 weeks for additional data collection.

Data from NIH PROMIS surveys, Fitbit and provided demographic

Title : Effect of Night Float Call on Sleep and Activity Patterns Among Anesthesia Residents
Approval Period: 08/19/2020 - 12/31/2999

information including age, sex and BMI, and number of previous night float periods previously completed. After association, data will be completely deidentified.

All data will be normalized to the participant's baseline values during the run-in week. The call week and post call week will be analyzed with a time series mixed effects model using R and/or NONMEM (a program for Nonlinear Mixed Effects Modeling). The effects of the above demographic variables will be assessed as potential covariates.

The intended goal of this project is to improve the current resident call structure within the anesthesia department (QI); however, we are applying for IRB approval because we believe that the data gathered about the impact of night float on sleep patterns and physician well-being can be generalized and we would want to publish this data in the future. We anticipate that this observational study will be the first of many studies looking at the effects of changing sleep patterns on activity and well-being

b) Explain how the above research procedures are the least risky that can be performed consistent with sound research design.

Our research protocol constitutes very low risk to participants because it does not require that they deviate from their usual behavior pattern. There is always a remote risk that data confidentiality will be breached. Steps taken to prevent that risk are data storage in Redcap and only using de identified data for analysis. All investigators have or will ([name]) complete CITI training prior to study initiation.

c) State if deception will be used. If so, provide the rationale and describe debriefing procedures. Since you will not be fully informing the participant in your consent process and form, complete an alteration of consent (in section 13). Submit a debriefing script (in section 16).

N/A

d) State if audio or video recording will occur. Describe what will become of the recording after use, e.g., shown at scientific meetings, erased. Describe the final disposition of the recordings.

N/A

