- d) If women, minorities, or children are not included, a clear compelling rationale must be provided (e.g., disease does not occur in children, drug or device would interfere with normal growth and development, etc.).**

n/a

- e) State the number, if any, of participants who are laboratory personnel, employees, and/or students. They should render the same written informed consent. If payment is allowed, they should also receive it. Please see Stanford University policy.**

All participants in the study will be employees of Stanford Hospital through Graduate Medical Education.

- f) State the number, if any, of participants who are healthy volunteers. Provide rationale for the inclusion of healthy volunteers in this study. Specify any risks to which participants may possibly be exposed. Specify the measures being taken to minimize the risks and the chance of harm to the volunteers and the additional safeguards that have been included in the protocol to protect their rights and welfare.**

All participants in this study will be healthy volunteers who are able to perform daily functions at work.

- g) How will you identify and recruit potential participants about the research study? (E.g., by: chart review; notified by treating physician; response to ad). All final or revised recruitment materials, flyers, etc. must be submitted to the IRB for review and approval before use. You may not contact potential participants prior to IRB approval. See Advertisements: Appropriate Language for Recruitment Material.**

Participants will be recruited via email solicitation once they have been scheduled for the above rotations.

- h) Inclusion and Exclusion Criteria.**

Identify inclusion criteria.

All residents who are scheduled for a night float rotation in the general Stanford Operating room or on OB anesthesia will be included.

Identify exclusion criteria.

Participants who report taking prescription medications that may effect alertness during the study period will not be enrolled.

- i) Describe your screening procedures, including how qualifying laboratory values will be obtained. If you are collecting personal health information prior to enrollment (e.g., telephone screening), please request a waiver of authorization for recruitment (in section 15).**

Demographic information will be collected via an electronic survey distributed at the beginning of the study period. We will not collect any PHI prior to enrollment.

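### No interval since the last night float is required, so the run-in week used as baseline can itself be a night float or recovery week, which biases the contrasts in either direction

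*Protocol*

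**What the plan says.** - **Eligibility.** Section 8h: "All residents who are scheduled for a night float rotation in the general Stanford Operating room or on OB anesthesia will be included". The only exclusion listed there is: "Participants who report taking prescription medications that may effect alertness during the study period will not be enrolled". Section 8j also bars residents who are in other studies. No passage sets a gap since the last night float or says what the run-in week must be free of.
- **Block structure.** Resources, item d: "each night float lasts 1 week and there will be one week run in before and one week of post call activities". Section 2a: "We will quantify the changes in sleep pattern and activity during the week before, during, and after the night float call week".
- **Reference.** Section 2a: "All data will be normalized to the participant's baseline values during the run-in week".
- **Effect periods.** Section 2a: "The call week and post call week will be analyzed with a time series mixed effects model". The week after night float is therefore one in which an effect is looked for.
- **Second rotation.** Modification, item 1, on residents previously recruited only from the general OR rotation: "we would also like to follow them when they are on their OB anesthesia rotation". The reason given is that they work night float there too.
- **Prior exposure.** Among the variables listed in section 2a, the only one on earlier night float is the "number of previous night float periods previously completed". That is a count and carries no date.

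**The concern.** The protocol measures the post-call week because the effect of night float may not end with the last shift. The same kind of week can nevertheless serve as the unaffected reference for the next block, since nothing in the eligibility rule prevents it. Two rotations with night float make neighbouring blocks possible, and the earlier one need not have been studied.

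An affected baseline distorts every outcome for that block, because each is normalized to the same week. A random effect for resident does not remove the error: it lies in the within-resident reference, not in the resident's general level. A count of earlier night float periods does not help either, because it does not show how recent the last one was.

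**Working it through.** The protocol gives no figure for carry-over, gap length or affected share, so there is nothing of its own to reproduce. Two things can be worked out: the direction of the bias, and how often it could arise under a stated roster.

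**1. Direction**

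Let B be the resident's unaffected level, E the loss in a night float week, and c the share of E still present in the week after. A positive c means persisting debt and a negative c means rebound. Assume that effects do not accumulate over blocks. The levels are then B − E in a night float week and B − cE in a post-call week.

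| Run-in week is | Call week minus run-in | Post-call week minus run-in |
|---|---|---|
| unaffected | −E | −cE |
| earlier post-call week | −E(1 − c) | 0 |
| earlier night float week | 0 | +E(1 − c) |

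- Run-in is a post-call week: at c = 0.25 the call-week contrast is 75% of E, and at c = 0.5 it is 50%. At c = −0.25 (rebound) it is 125%.
- Run-in is a night float week: the call-week contrast is about zero. The post-call contrast is recovery minus night float, which is generally not zero and, for c between 0 and 1, has the opposite sign to the true contrast.

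The protocol does not say whether normalizing means subtracting or dividing. Dividing gives the same direction. Take B = 7 h and E = 1 h (both assumptions). The true ratio is 6/7 = 0.857. With c = 0.5 it becomes 6/6.5 = 0.923, a smaller apparent loss. With c = −0.25 it becomes 6/7.25 = 0.828, a larger one.

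**2. Frequency under an assumed roster**

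Assumptions, none of them in the protocol: one night float week per resident in each 4-week rotation, the week placed at random, and OR and OB months consecutive. Put the first night float in week i = 1 to 4 and the second in week j = 5 to 8, giving 16 equally likely pairs. The second run-in is week j − 1.

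- It is the earlier night float week if j − i = 1: (4,5), 1 pair.
- It is the earlier post-call week if j − i = 2: (3,5) and (4,6), 2 pairs.
- Affected second blocks: 3/16 = 18.75%.
- Over both blocks of such a resident, with the first baseline taken as clean: 3/32 = 9.4%.
- If rosters never place two night float weeks back to back, (4,5) drops out: 2/15 = 13% of second blocks.
- If the rotations are well separated: 0%.

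**3. Average effect on the call-week contrast**

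Under the 16-pair roster, the ratio to the true effect among second blocks is 1 − 1/16 − (2/16)c. This gives 0.906 at c = 0.25, 0.875 at c = 0.5 and 0.969 at c = −0.25. Over both blocks it is 1 − 1/32 − (2/32)c, which is 0.9375 at c = 0.5.

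**The case against.** The strongest reply is that the risk is narrow and may already be manageable.

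- **The second rotation may be mainly a recruitment source.** Resources, item e, counts four residents on each rotation to reach up to eight participants a month, which need not mean repeat follow-up. If the optional three extra weeks in section 2a form a second block directly after the first, night float falls in weeks 2 and 5. The second run-in is then week 4, after a full post-call week. This stands, and it confines the problem mainly to earlier blocks that were not studied or that lie closer. It does not remove it, because no spacing is fixed.
- **A reader might infer that affected baselines cannot be identified.** The documents do not support that. The demographic survey is an attachment that is not shown and may ask for a date, and residents are recruited from a schedule that could be consulted. What can be said is that the variables listed in section 2a include no date.
- **A reader might infer that carry-over always shrinks the effect.** It does so only if the effect persists in the same direction. Catch-up sleep in the recovery week would inflate the estimated sleep loss.
- **A reader might take 19% as the share of the study affected.** It is the share of second blocks under an assumed roster with consecutive months. The protocol gives neither the roster nor the number of residents with such months.
- **Dropping blocks is not free.** The figure of eight a month counts places, not distinct residents. Section 8b speaks of a limited pool, and twelve participants had been enrolled at the time of the modification.
- **The reference week for overlapping blocks could be set in an analysis plan that is not shown.** That is fair for the analysis rule. Eligibility and data collection are fixed here, and an analysis plan can use the time since the last night float only if it was recorded or can still be looked up.

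**Conclusion.** The concern holds in limited form. As written, the protocol allows an affected week to serve as the clean baseline, and the variables it lists do not show when this has happened. The bias has no fixed direction. It is large for an individual affected block: the call-week contrast falls to half at c = 0.5 and to about zero if the run-in is itself a night float week. On average it is modest under the illustrative roster, about 6% over both blocks at c = 0.5 (1 − 0.9375). The true share affected is unknown and may be nil if blocks are well apart. The conclusion rests on the missing interval, the single-week reference and the protocol's own treatment of the post-call week as an effect period. It does not rest on the assumed roster. This is an inexpensive improvement to the design, not a defect that undermines the study.

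**What to change.** 1. Record the date of each resident's last night float or overnight shift before the run-in week. Put it on the demographic survey, check it against the rota, and do so before the data are de-identified.
2. Add to section 8h that a run-in week is not used as baseline if it contains night float or directly follows a night float week. Either study a later block of that resident, or use the resident's earlier clean run-in week if one was recorded. This removes all three affected pairs in the count above and still admits a second block in weeks 4 to 6. It governs which weeks serve as reference and does not change how residents are rostered.
3. If such blocks must be kept because the pool is limited, flag them and report the analysis with and without them.

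The cost is one survey item, one sentence in section 8h and a few delayed or unused blocks. The one-week gap mirrors the protocol's own post-call window. It is a judgement, since the documents contain no data from which a gap length could be derived.
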